C.2. GLUCO-CABG Trial:²⁴ in this RCT we aimed to determine whether intensive BG control (target: 100-140 mg/dl) could reduce perioperative complications compared to conservative BG control (141-180 mg/dl) in hyperglycemic patients undergoing CABG. A total of 302 patients were randomized to intensive (n=151) or conservative (n=151) glucose control. The mean ICU daily BG was 132 ± 14 mg/dl (IQR 124-139) in the intensive and 154 ± 20 mg/dl (IQR 142-164) in the conservative group ($p < 0.001$). Overall, we observed a similar number of patients in the intensive and conservative groups experiencing ≥ 1 complications (42% vs. 52%, $p = 0.08$). We observed no differences in the composite or individual complications in patients with DM; however, the composite of complications was lower in non-DM patients with stress-hyperglycemia assigned to the intensive group, $p = 0.008$, (Fig.2). Since all patients enrolled GLUCO-CABG patients had stress-hyperglycemia, we recently *analyzed phenotypic and biological characteristics of non-diabetic individuals at risk for perioperative stress hyperglycemia during CABG*. The two most important features in patients who developed >2 episodes of BG >140 mg/dL were older age (67.0 ± 9.2 vs 59.1 ± 9.4 , $p = 0.004$) and higher BMI (28.9 ± 5.8 vs 26.1 ± 4.3 , $p = 0.06$). All six patients older than 50 years and BMI >30 kg/m² developed hyperglycemia. These characteristics were confirmed in an additional cohort (i.e. age >45 years). Older age and obesity are well-established risk factors for insulin resistance and DM.

C.3. Inflammatory markers during CABG: Circulating levels of cortisol, inflammatory and oxidative stress markers increase for several days in the perioperative period (Fig. 3). No difference was observed between conservative and intensive insulin therapy groups in the perioperative period of patients undergoing CABG surgery. Changes in these markers did not explain the benefits associated with tighter glycemic control with insulin therapy.³

C.4. GLP-1 RA safety and non-inferiority to insulin therapy.

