Exclusion criteria: a) Hyperglycemia (BG > 125 mg/dl or HbA1c $> 6.5\%$) or previous treatment with antidiabetic agents; b) impaired renal function (GFR < 30 ml/min) or clinically significant hepatic failure; c) subjects with gastrointestinal obstruction expected to require gastrointestinal suction; d) patients with clinically relevant pancreatic or gallbladder disease; e) treatment with oral or injectable corticosteroid; f) mental condition rendering the subject unable to understand the possible consequences of the study; g) pregnancy or breast-feeding at time of enrollment. Additional considerations are outlined in the Human Subjects section.

Aim 2.1 Prevention of hyperglycemia (primary endpoint):

The primary endpoint of this exploratory study is to compare the frequency of stress-hyperglycemia defined as any post-CABG hospital-obtained BG > 140 mg/dl between patients randomized to dulaglutide or placebo.

Aim 2.2 Secondary Endpoints: To determine the difference between groups in mean BG level in the ICU.

Additional endpoints include differences between treatment groups on: 1) the number of patients with stress-hyperglycemia requiring rescue therapy with SC insulin after discontinuation of CII; 2) need for CII treatment of hyperglycemia in the ICU; 3) mean ICU and floor BG concentration; 4) mean insulin dose during ICU (insulin infusion per hour (unit/hour) and per day); 5) duration of CII (hours); 6) days of SC insulin after discontinuation of CII; 7) amount of SC insulin in ICU and non-ICU stay; 8) hyperglycemic events (BG ≥ 200 mg/dl) in ICU and non-ICU; 9) hypoglycemic events in ICU and non-ICU (< 70 , < 54 , and < 40 mg/dl); 10) composite of mortality and complications including sternal wound infection, bacteremia, pneumonia, acute kidney injury, and acute myocardial infarction; 11) gastrointestinal adverse events (nausea, vomiting, ileus, pancreatitis); 12) ICU and hospital LOS, and ICU readmissions; 13) cerebrovascular events; 14) ICU and hospital mortality.

Methods for Aims 2.1 and 2.2:

Treatment Groups: Patients will be randomized at pre-surgery/anesthesia visit. Patients without a history of DM will receive a single injection of dulaglutide/placebo 1-3 days prior to surgery (Fig. 8).

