Analysis: The primary endpoint of Aim 2 is the frequency of stress-hyperglycemia ($BG > 140$ mg/dl) requiring insulin therapy during the postoperative period (Aim 2.1). We will use two-sided Chi-square test or Fisher's exact test for the primary outcome. In Aim 2.2 we will compare the difference in mean BG upon ICU arrival and the frequency of rescue therapy with SC insulin after transition to regular floor. We will also explore differences in complications between groups. Secondary outcomes of interest can be a binary outcome (e.g. whether CII is needed in ICU), or a count outcome (e.g. number of perioperative complications), or a continuous outcome (e.g. mean ICU BG concentration). We will adopt the same strategy proposed for the primary outcome to analyze any binary secondary outcomes. For secondary outcomes measured as counts, we plan to use nonparametric tests such as Krustal-Wallis tests. Univariate Poisson regression (or Negative Binomial regression) will be performed to estimate the marginal treatment effect. In addition, we will also conduct multivariate Poisson regression (or Negative Binomial regression) to assess the outcome differences between the two study groups with potential confounders considered. For secondary endpoints that produce continuous outcomes, we will use two-sample t-tests or nonparametric Wilcoxon tests to compare study groups.

Transformations will be applied if normality violation is detected.

Aim 2.3. To compare changes in metabolites and biomarkers in response to dulaglutide or placebo (measured in Aims 1.1 and 1.2), as well as beta-cell function and insulin resistance estimates.

Methods: Biomarkers and assessment of candidate metabolites will follow the same procedures as specified in Aim 1. Surrogates of beta cell function and insulin resistance will be derived from glucose, insulin, and c-peptide measurements acquired during the perioperative period.

[figure not shown]

Figure 8. Treatment groups in Aim 2. Patients will be assigned to receive dulaglutide or placebo 1-3 days before surgery.

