- Data collection and data entry. Study members will enter baseline and daily data for this study into data collection paper forms and into an electronic database provided by the Emory Research Information Technology Department. Baseline data will include demographics/history form (subject gender, date of birth, ethnicity, dates of hospitalization and operation, history of diabetes, and comorbid conditions, body weight, BMI, smoking status, type of surgery, APACHE score. Daily information will be collected on treatment (insulin IV or SC and dosage, antibiotics, use of corticosteroids), nutrition support, BG and laboratory values, hospital complications and adverse events, and length of ICU and hospital stay.

E.1.3. Potential Risks

- **Potential Risks/Discomforts:**
 - a. Venipuncture: There is some minor discomfort and risk of mild bruising during venipuncture. Standard sterile techniques will be used during phlebotomy; thus, infection is unlikely. Disposable pre-sterilized needles and syringes will be used for all blood drawing in this study; needles and syringes will not be reused. Discomforts associated with venipuncture are rapidly reversible. Approximately 40 mL of blood will be obtained for all the blood measurements proposed.

- b. Hypoglycemia: In our previous ICU studies, we observed that <10% of cardiac surgery subjects during CII and 20-30% during SC insulin experienced hypoglycemia. No episodes of severe hypoglycemia were observed during CII in our study. The use of insulin in combination with GLP1-RA may increase the risk of hypoglycemia. The number of mild (≤ 70 mg/dL) and severe hypoglycemia (≤ 40 mg/dL) and clinical consequences (neurological and cardiovascular) will be compared between groups. Treatment of hypoglycemia: hypoglycemia, defined as a BG <70 mg/dL will be treated by a standard hypoglycemia protocol available at each hospital.
- c. Hyperglycemia: it is very likely that a high proportion of patients randomized to placebo develop hyperglycemia. All subjects with hyperglycemia (in both groups) will be treated by standard protocols in the ICU units at each hospital. We expect that ~50-60% of subjects randomized to placebo will experience one or more episodes of hyperglycemia. The frequency of severe hyperglycemia will be analyzed statistically.

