- **Risk/Importance Assessment:** The anticipated benefits of the proposed research study outweigh the potential risks to participating subjects. The potential for serious adverse effects is small and the potential benefit to society is high enough for the studies to proceed.

E.1.7 Data and Safety Monitoring Plan (DSMP): Please see DSMP provided as a separate document.

E.1.8 ClinicalTrials.gov Requirement: This clinical trial will be registered on ClinicalTrials.gov. Final results will be published on this site.

E.1.9 Statistical Considerations

Sample Size Calculation and Power Analysis: with a Wilcoxon test, for an effect size >1 at alpha=0.05 and power=0.80, the proposed sample size of N=50 for this experiment will be more than adequate for the main objective of identifying differentially expressed metabolites and pathways in Aim 1, as shown in previous studies.^{134,138} For Aim 2 we assumed N=60. No preliminary data on prevention of hyperglycemia is available. Assuming an effect size of ~0.50 on hyperglycemia prevention with χ^2 goodness of fit for contingency tables, power 80%, alpha=0.05, a total of 52 patients would be needed. In our previous RCT (GLUCO-CABG⁴) non-DM patients in the conservative group had a mean BG 143mg/dl vs. 127mg/dl in the intensive group. This difference was associated with a lower composite score of complications in the intensive group. It is reasonable to assume the standard deviation of the mean BG is bounded around 40 mg/dl. With two-sample t tests or Wilcoxon tests, alpha=0.05, 25 subjects for each arm would be needed to ensure 80% power to reject the hypothesis that the mean BG in patients treated with dulaglutide is not 16 mg/dl lower compared to placebo. Accounting for ~15% attrition rate this leads to a final total sample size estimate of 60 patients for both considerations. This study is not powered to assess differences in hospital complications between groups.

Research Timeline	Yr1	Yr2	Yr3	Yr4	Yr5
Aim 1. Case-Control					
Study initiation (IRB)	x				
Recruitment / sample collection	xx	xx	xxx	xx	
Lab assays / data processing				xxx	xxx
Analysis / manuscript preparation				xxx	xxx
Aim 2. Clinical Trial					
Study initiation (IRB)	x				
Randomization / sample collection	xx	xxx	xx	xx	
Lab assays / data processing				xxx	xxx
Analysis / manuscript preparation				xxx	xxx

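### The binary primary endpoint is tested without adjusting for age and BMI, which the plan itself names as leading features and collects; adjustment is a cheap gain of about 4 to 7 power points if those differences carry over, and about 2 points or less if they do not hold up

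*Combined protocol and SAP*

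**What the plan says.** The Analysis paragraph of section D2 (Aims 2.1 and 2.2) states: "We will use two-sided Chi-square test or Fisher's exact test for the primary outcome". It gives no rule for choosing between the two tests, and no effect estimate or interval for the primary outcome. Binary secondary outcomes follow the same approach. Covariates appear only in the Poisson or negative binomial model for count outcomes. The documents describe no stratified randomisation.

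Section C.2 reports the team's earlier data: "The two most important features in patients who developed >2 episodes of BG >140 mg/dL were older age" (67.0 ± 9.2 v 59.1 ± 9.4 years, p = 0.004), followed by higher BMI (28.9 ± 5.8 v 26.1 ± 4.3, p = 0.06). Both are recorded before surgery. The data table in section E.1.2 lists age and BMI, and the data-entry text says: "Baseline data will include demographics/history form (subject gender, date of birth", with BMI later in the same list.

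The endpoint itself is worded in two ways. Aim 2.1 uses "any post-CABG hospital-obtained BG > 140 mg/dl between patients randomized to dulaglutide or placebo"; the Analysis paragraph counts only hyperglycaemia that needed insulin.

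**The concern.** Aim 2 is meant to yield preliminary estimates of the treatment effect from 30 v 30 patients. At that size, chance differences between arms in age and BMI add noise to the comparison. Neither the randomisation nor the primary analysis, as described, removes it. The plan uses age and BMI to select patients at high risk, then leaves them out of the primary comparison. At stake is precision and some power, not the validity of the test.

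**Working it through.** **The plan's own power figure.** Section E.1.9 says: "Assuming an effect size of ~0.50 on hyperglycemia prevention with" a chi-square method, and "power 80%, alpha=0.05, a total of 52 patients would be needed". The metric and the event rates are not given. If 0.50 is Cohen's w in a 2x2 table (1 df), N = (1.960 + 0.842)² / 0.50² = 7.85 / 0.25 = 31.4, so 32 rather than 52; 52 appears only with 5 df. On that reading chi-square power is 95% at N = 52 and 97% at N = 60. If 0.50 is instead a 50% relative reduction, 60% v 30% needs 42 per arm and power at 30 per arm is about 65%. The room for gain therefore depends on a reading the plan does not settle, and both are carried below.

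**Strength of the predictors (section C.2).**
- Age: pooled variance (9.2² + 9.4²)/2 = 86.5. Standardised difference 7.9/9.30 = 0.85. Log-odds slope 7.9/86.5 = 0.091 per year.
- BMI: pooled variance (5.8² + 4.3²)/2 = 26.07. Standardised difference 2.8/5.11 = 0.55. Slope 2.8/26.07 = 0.107 per kg/m².
- With both, taken as independent, D² = 0.85² + 0.55² ≈ 1.02. At 60% prevalence, R² = 0.24 × 1.02 / (1 + 0.24 × 1.02) ≈ 0.20. Inside the eligibility limits (age 40 to 80, BMI ≥25) R² falls to about 0.16.

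**Approximate gain.** Adjusted power = Φ((z_power + z_α)/√(1 − R²) − z_α). From 80% with R² = 0.16: 2.802/0.917 − 1.960 = 1.097, which gives 86.4%, or +6.4 points. At half slopes R² is about 0.05 and the gain is +2.0.

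**Simulation.** 30 per arm, 3,000 to 4,000 trials per scenario. Assumed population: age N(64, 10) limited to 40–80, BMI N(28, 5.5) limited to ≥25, independent. The adjusted analysis is a logistic model with arm, age and BMI, standardised to a risk difference, with an influence-function standard error and t on 60 − 4 = 56 df. Arm rates are assumptions, because the plan gives none for dulaglutide. Its placebo figures are about 50–60% in section E.1.3 and 60–80% in the Specific Aims. Representative results at full C.2 slopes:

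| Placebo v dulaglutide | Fisher | Chi-square | Adjusted | Adjusted − chi-square |
|---|---|---|---|---|
| 55% v 27.5% | 48.1% | 59.0% | 65.6% | +6.6 |
| 60% v 30% | 55.5% | 66.7% | 72.5% | +5.8 |
| 80% v 50% | 61.1% | 69.7% | 75.9% | +6.2 |
| 60% v 25% | 71% | 80% | 85% | +5 |

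Monte Carlo error is just under 1 point per power figure. Over repeat runs chi-square power lay at about 57–80% and the gain at about 4–7 points.

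**When the assumptions change.**
- Half slopes, 60% v 30%: 66.7% to 68.0% (+1.3).
- No covariate effect, 60% v 30%: 67.0% to 65.9% (−1.1).
- w = 0.50, taken as 75% v 25%: 96.3% to 98.3% at 26 per arm (+2.0) and 98.4% to 99.1% at 30 per arm (+0.7).

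**Type I error** (null at 60%): Fisher 2.8%, chi-square 5.5%, adjusted 5.5%. A likelihood-ratio test from the same logistic model ran slightly high, at 5.8–6.2%.

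**Fisher against chi-square.** From the table, the gaps are 59.0 − 48.1 = 10.9, 66.7 − 55.5 = 11.2, 69.7 − 61.1 = 8.6 and 80 − 71 = 9 points. These involve no covariates.

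**The case against.** The unadjusted test is valid under randomisation, and the plan calls the study exploratory. The predictor evidence is thin. Section C.2 concerns more than two episodes, whereas the trial endpoint is any reading above 140 mg/dl, or one needing insulin. BMI has p = 0.06. The reported SDs and p-values imply roughly 25 per group (an inference that assumes equal groups), so the age gap is about 7.9 ± 5.3 years and half-size slopes are well within range. Features singled out as most important also tend to be overstated; the text says they were confirmed in a further cohort but gives no effect sizes there. Eligibility already narrows both variables. The D2 rationale speaks of obese patients over 50, which differs from its inclusion criteria; with age 50–80 and BMI ≥30 assumed, the gain is +3.5 points at full slopes and +0.6 at half. For 60% v 30%, the simulated SD of the risk difference falls only from 0.123 to 0.115, so a 95% half-width of 1.96 × 0.123 = 24 points becomes 1.96 × 0.115 = 23.

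All of this stands as a limit on the size of the gain. It does not remove the case for adjusting: the covariates are already collected, the risk is about 1 point of power, and the variance reduction of about 12% is worth roughly eight patients (60/0.88 ≈ 68).

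A reader might infer that at least 6 points are being lost. The documents do not support a floor: half slopes, no carry-over, or w = 0.50 each give about 2 points or less. A reader might also take the 15- to 18-point gap between Fisher and the adjusted analysis as the price of missing covariates. Most of it is Fisher's conservatism, and choosing chi-square recovers that part.

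**Conclusion.** The point holds as one of efficiency, and the current test is not wrong. With assumed rates giving about 57–80% chi-square power at 30 per arm, adjusting for age and BMI adds about 4–7 points if the C.2 differences apply to the primary endpoint. It adds about 1–2 points if they are half as strong, and nothing or about −1 if they do not apply. It also adds about 1–2 points if 0.50 is w in a 2x2 table, where chi-square power is already above 95%. Fisher's test separately costs about 8–11 points in the first set of scenarios, with actual type I error of about 2.5–3%. These figures rest on assumed arm rates, an assumed age and BMI distribution, and slopes borrowed from a proxy outcome. The importance lies between optional and recommended.

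**What to change.** In the D2 Analysis paragraph, before outcome data are seen, make the primary analysis a risk difference adjusted for age and BMI. Fit a logistic model with arm and both covariates as continuous terms, and standardise over all randomised patients. Use a robust or influence-function standard error with small-sample degrees of freedom, and report the estimate with its 95% interval. Keep one named unadjusted 2x2 test as a sensitivity analysis, and fall back to the unadjusted risk difference if the logistic fit separates.

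The two wordings of the primary endpoint need to be reconciled in any case; the adjustment applies to whichever is kept.

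Cost: a few lines of plan text and code, and no new data. The price is two extra model parameters and about 1 point of power if the covariates turn out not to be prognostic.

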will be possible using innovative ultra-high resolution mass spectrometry (HRMS) with liquid chromatography (LC) and gas chromatography (GC) and advanced data extraction algorithms. LC-HRMS will also measure >2000 metabolomic intermediates in plasma at the time of surgery and at follow-up, providing coverage of >85% of human metabolic pathways. ***The overall hypotheses are that candidate metabolites such as: ceramides, acylcarnitines, and branched-chain amino acids (BCAAs) are associated with incident stress hyperglycemia, and that hyperglycemia leads to changes in path-specific biomarkers related to CV risk. In addition, exposure to an agent associated with low risk of hypoglycemia can positively affect the trajectory of metabolic changes during acute surgical stress.***

Baseline measurements: Samples will be collected up to seven days prior to scheduled CABG surgery. Blood samples will be processed by the CRN Laboratory and stored at -80°C until ready for batch analysis. Fasting plasma metabolomics analysis will be performed using high-resolution metabolomics (HRM) methods established in Co-mentor [name]' laboratory. Samples for measurement of biomarkers, glucose, cortisol, glucagon, insulin and c-peptide will also be collected. Indexes of insulin sensitivity/insulin resistance: will be derived from glucose, insulin and c-peptide values. Indexes of insulin secretion: pancreatic β-cell insulin secretion capacity will be assessed with HOMA-B.

Sources of materials: Research material will include medical history, demographic information, and complications obtained both from subjects, medical record, and study blood samples.

Data collected: Data to be collected is detailed in **Table 1** below, along with the source of the data. Baseline and daily information will be entered by [name] or a study coordinator into data collection paper forms and into an electronic database (REDCap) provided by the Emory Research Information Technology Department.

Table. Data to be collected and source

Data Item	Source
-Vitals (e.g. blood pressure, pulse, temperature)	Medical Exam
-Height, weight, BMI	Manual stadiometer and digital scale
-Demographic Information (e.g. age, race)	Self-report and medical records
-Medical history (e.g., comorbidities, surgeries)	Self-report and medical records
-Social history (e.g., education, smoking, alcohol use)	Self-report and medical records
-Indexes of insulin secretion, resistance and sensitivity	serial blood draws

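### Mean ICU glucose is compared only by an unadjusted t or Wilcoxon test; a short pre-specified ANCOVA would probably recover a modest amount of precision at little cost

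*Combined protocol and SAP*

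**What the plan says.** Section D2, Analysis (Aims 2.1 and 2.2), gives one rule for continuous outcomes: "For secondary endpoints that produce continuous outcomes, we will use two-sample t-tests or nonparametric Wilcoxon tests to compare study groups". Transformation is allowed if normality fails. Mean ICU BG is that paragraph's own example of a continuous outcome, and it heads the list under Aim 2.2.

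The same paragraph treats count outcomes differently. They also receive a Poisson or negative binomial model to "assess the outcome differences between the two study groups with potential confounders considered". No such model is planned for a continuous glycemic endpoint, there or elsewhere. The adjustment for gender and smoking in section D1 belongs to the case-control study.

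The covariates are available. On baseline sampling, section E.1.2 says: "Samples for measurement of biomarkers, glucose, cortisol, glucagon, insulin and c-peptide will also be collected". Its data table also lists age and BMI. Section C.2 reports, from the group's own cohort: "The two most important features in patients who developed >2 episodes of BG >140 mg/dL were older age" (67.0 against 59.1 years), followed by higher BMI (28.9 against 26.1, p = 0.06).

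Section E.1.9 uses mean BG as one of two justifications for the sample size: "With two-sample t tests or Wilcoxon tests, alpha=0.05, 25 subjects for each arm would be needed to ensure 80% power". The difference between arms assumed there is 16 mg/dl. On the SD the section says: "It is reasonable to assume the standard deviation of the mean BG is bounded around 40 mg/dl".

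**The concern.** Aim 2 is framed as a source of preliminary estimates, so the width of the interval around the treatment difference is much of what it delivers. With 60 patients, variance explained by baseline characteristics is worth removing if that can be done cheaply. The plan identifies two prognostic variables, records them before surgery, and then leaves them out of the comparison of its lead continuous endpoint, while allowing adjustment for counts.

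No stratification is described. With 30 per arm, the difference between arms in a standardized covariate has standard error √(2/30) = 0.258. A gap above 0.25 SD in a given covariate therefore arises by chance about one time in three (0.25/0.258 = 0.97; two-sided normal probability about 0.33). The t test allows for such gaps on average through its standard error, but does not correct the estimate for the gap that actually occurred.

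**Working it through.** **Inputs.** Difference 16 mg/dl, SD 40 mg/dl, alpha 0.05, power 80%, 25 per arm, about 15% attrition, N = 60 (E.1.9); 30 per arm (E.1.1). For the SD, section C.2 reports: "The mean ICU daily BG was 132 ± 14 mg/dl (IQR 124-139) in the intensive and 154 ± 20 mg/dl"; I therefore also use SD 20. Sidedness is not stated for the t or Wilcoxon tests; two-sided is assumed. R² between the covariates and mean ICU BG is not given and is varied.

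**Step 1: the plan's own figure.** n per arm = 2(1.96 + 0.842)² × SD²/16².
- SD 40: 15.70 × 6.25 = 98.1, so 99 per arm (100 by exact t; 78 one-sided, normal).
- SD 20: 15.70 × 1.5625 = 24.5, so 25 per arm (26 by exact t).

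The stated 25 does not follow from SD 40; it matches SD 20. Attrition agrees: 50/0.85 = 58.8, close to 60. Because of this mismatch, both SDs are carried below.

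**Step 2: what the documents suggest about R².** Standardized differences from C.2:
- Age: (67.0 − 59.1)/√((9.2² + 9.4²)/2) = 7.9/9.30 = 0.85.
- BMI: (28.9 − 26.1)/√((5.8² + 4.3²)/2) = 2.8/5.11 = 0.55.

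With R² = d²/(d² + 1/[p(1 − p)]), where p is the share in one group (assumed 0.5 to 0.8), age gives about 0.10 to 0.15 and BMI about 0.05 to 0.07, each taken singly. These concern having more than two BG values above 140 mg/dl, not mean ICU BG, so they are only a guide.

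**Step 3: net effect of ANCOVA.** Estimating k covariates has a price. Variance ratio, adjusted to unadjusted = (1 − R²) × [1 + k/(N − k − 3)]. For N = 60 the bracket is 1.036 (k = 2), 1.056 (k = 3), 1.075 (k = 4) and 1.163 (k = 8). Break-even R² is 1 − 1/bracket: about 3.5%, 5%, 7% and 14%.

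| R² | k = 2 | k = 3 | k = 4 | k = 8 |
|---|---|---|---|---|
| 0.10 | 0.93 | 0.95 | 0.97 | 1.05 |
| 0.15 | 0.88 | 0.90 | 0.91 | 0.99 |
| 0.20 | 0.83 | 0.84 | 0.86 | 0.93 |

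**Step 4: power for 16 mg/dl** (noncentral t, N − 2 − k degrees of freedom, k = 2).

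| | Unadjusted | R² 0.10 | R² 0.15 | R² 0.20 |
|---|---|---|---|---|
| 30 per arm, SD 40 | 33% | 35% | 37% | 39% |
| 30 per arm, SD 20 | 86% | 88% | 90% | 92% |
| 25 per arm, SD 40 | 28% | 30% | 31% | 33% |
| 25 per arm, SD 20 | 79% | 82% | 84% | 86% |

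**Step 5: interval width.** The unadjusted standard error at 30 per arm is SD × √(2/30): 10.3 mg/dl at SD 40 and 5.2 at SD 20, giving 95% half-widths of about 20.7 and 10.3. At R² 0.15 with k = 2 the standard error is multiplied by √0.881 = 0.94, giving about 19.4 and 9.7.

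**The case against.** The strongest reply is that nothing here is wrong. In a randomised comparison the unadjusted test is valid, its standard error already covers chance imbalance, and the endpoint is secondary in a study the plan itself calls exploratory. That stands: this is a matter of efficiency, not a correction of an error.

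The reply also holds that the gain is unproven. No section relates any baseline variable to mean ICU BG. Section C.2 supports only age and BMI, for a different outcome. Eligibility limits narrow the ranges of glucose, HbA1c, age and BMI. Insulin titrated to a target in the ICU may compress mean BG and weaken its link with baseline. All of this stands, and it is why the gain is called modest and the covariate list must be short.

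A reader might infer more than the documents support:
- **That variance falls by the full R².** This ignores the cost of estimating covariates. With four covariates and R² 0.10, the net reduction is 3%, not 10%.
- **That every baseline variable should go in.** With about eight covariates, precision is lost unless R² exceeds about 14%. HbA1c is an eligibility value and is not named in the E.1.2 data table.
- **That biomarker and metabolite comparisons share the fault.** Aim 2.3 assigns these to linear mixed models, LIMMA and related methods, not t tests. Count outcomes already have an adjusted model.
- **That adjustment rescues the sample size.** At SD 40, even R² 0.50 would need 50 per arm before any covariate penalty (98.1 × 0.5 = 49.1).

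**Conclusion.** The point holds as a cheap improvement to the analysis of mean ICU BG. The planned test is valid but gives up some precision that variables already recorded could supply. With two covariates and 30 per arm, the net variance reduction is about 7% to 17% over R² 0.10 to 0.20. That is 2 to 6 percentage points of power at either SD, and a 95% interval about 3% to 9% narrower.

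These figures assume an R² that the documents do not give, two-sided testing and full follow-up; with 25 completers per arm the gains are similar. If the covariates explain less than about 3.5% of the variance, adjustment loses a little precision: at most about 4% more variance with two covariates (bracket 1.036). The conflict between SD 40 and 25 per arm in section E.1.9 is a larger and separate problem, which this change does not repair.

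**What to change.** In section D2, Analysis, pre-specify a linear model (ANCOVA) for mean ICU BG with treatment and two or three named covariates: age, BMI and, optionally, baseline glucose. Report the adjusted difference with its 95% CI. Keep the t or Wilcoxon test as a sensitivity analysis, and fix the covariate list before anyone sees outcomes by arm.

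Two details need wording:
- Define the outcome. Aim 2.2 names mean BG in the ICU, while the analysis paragraph speaks of mean BG on ICU arrival.
- If baseline glucose is used, require a value drawn before the study injection. The baseline window of up to seven days before surgery does not by itself ensure this, because the injection is given one to three days before surgery.

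The cost is a few sentences of analysis text. No new data are needed for age and BMI. The only statistical downside is the small loss described above if the covariates turn out to be nearly uninformative.
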